6.3.2 Dose adjustments for QTcF prolongation

Not applicable

6.3.3 Follow-up for toxicities

Patients whose treatment is interrupted or permanently discontinued due to an adverse event or abnormal laboratory value must be followed for at least 30 days. All unresolved toxicities should be followed by the investigator until CTCAE Grade ≤ 1 , return to baseline, stabilization or the subject is lost to follow-up.

6.3.3.1 Follow up on potential drug-induced liver injury (DILI) cases

Patients with transaminase increase combined with TBIL increase may be indicative of potential DILI, and should be considered as clinically important events.

The threshold for potential DILI may depend on the patient's baseline AST/ALT and TBIL value; patients meeting any of the following criteria will require further follow-up as outlined below:

- For patients with normal ALT and AST and TBIL value at baseline: AST or ALT $> 3.0 \times$ ULN combined with TBIL $> 2.0 \times$ ULN
- For patients with elevated AST or ALT or TBIL value at baseline: [AST or ALT $> 2 \times$ baseline AND $> 3.0 \times$ ULN] OR [AST or ALT $> 8.0 \times$ ULN], combined with [TBIL $> 2 \times$ baseline AND $> 2.0 \times$ ULN]

Medical review needs to ensure that liver test elevations are not caused by cholestasis, defined as ALP elevation $> 2.0 \times$ ULN with R value < 2 in patients without bone metastasis, or elevation of ALP liver fraction in patients with bone metastasis.

Note: (The R value is calculated by dividing the ALT by the ALP, using multiples of the ULN for both values. It denotes whether the relative pattern of ALT and/or ALP elevation is due to cholestatic (R ≤ 2), hepatocellular (R ≥ 5), or mixed (R > 2 and < 5) liver injury).

In the absence of cholestasis, these patients should be immediately discontinued from study drug treatment, and repeat LFT testing as soon as possible, preferably within 48 hours from the awareness of the abnormal results. The evaluation should include laboratory tests, detailed history, physical assessment and the possibility of liver metastasis or new liver lesions, obstructions/compressions, etc. Data and test results must be entered in the hepatotoxicity follow up test procedures eCRFs available in the clinical database.

1. Laboratory tests should include ALT, AST, albumin, creatine kinase, total bilirubin, direct and indirect bilirubin, GGT, prothrombin time (PT)/INR and alkaline phosphatase.
2. A detailed history, including relevant information, such as review of ethanol, concomitant medications, herbal remedies, supplement consumption, history of any pre-existing liver conditions or risk factors, should be collected.
3. Further testing for acute hepatitis A, B, C or E infection and liver imaging (e.g. biliary tract) may be warranted.
4. Obtain PK sample, as close as possible to last dose of study drug, if PK analysis is performed in the study.
5. Additional testing for other hepatotropic viral infection (CMV, EBV or HSV), autoimmune hepatitis or liver biopsy may be considered as clinically indicated or after consultation with specialist/hepatologist.

All cases confirmed on repeat testing meeting the laboratory criteria defined above, with no other alternative cause for LFT abnormalities identified should be considered as “medically significant”, thus, met the definition of SAE (Section 8.2.1) and reported as SAE using the term “potential drug-induced liver injury”. All events should be followed up with the outcome clearly documented.

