Study treatment discontinuation	Point/time when patient permanently stops taking study treatment for any reason
Subject Number (Subject No.)	A unique identifying number assigned to each patient/subject/healthy volunteer who enrolls in the study
Treatment emergent adverse events	Adverse events that a subject experiences within 30d after last dose of study treatment
Variable	Identifier used in the data analysis; derived directly or indirectly from data collected using specified assessments at specified timepoints
Withdrawal of consent	Withdrawal of consent occurs only when a patient does not want to participate in the study any longer, and does not want any further visits or assessments, and does not want any further study related contact

Amendment 1 (25-Apr-2018)

Amendment rationale

As of 25-Apr-2018, seven patients have been enrolled into the study.

Deferasirox FCT 90 mg, 180 mg, and 360 mg (Deferasirox FCT), is commercially available in some participating countries but not in all countries.

The purpose of this amendment is to enable Novartis Drug Supply Management to supply labeled study drug to countries where Deferasirox FCT is not commercially available and also to enable countries where Deferasirox FCT is commercially available to follow their local processes for using commercial products in clinical trials.

Two guidance were provided related to collection of Observer Reported Outcomes (ObsROs)

- The GI symptom questionnaire was removed from the Week 1 day 1 visit because for all 3 questionnaires, the Screening visit 1 ObsRO will be considered baseline. Additionally, patients who are on prior chelation therapy other than deferasirox are not able to complete the GI questionnaires at Week 1 day 1 because of the 5 day washout period required. The questionnaires investigate the impact of chelation treatment received 7 days prior to the visit.
- Chelation naïve patients and patients treated with chelation therapy who stopped treatment more than 7 days prior to Screening visit 1 (SV1) will not complete ObsROs questionnaires at SV1. The questionnaires investigate impact of chelation treatment received within 7 days prior to SV1 and as such are not applicable to naive patients and patients treated with chelation therapy who stopped treatment more than 7 days prior to SV1.

In addition, some updates have been made to provide further clarification on some aspects of the study as listed below.

Changes to the protocol

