6.1.4 Guidelines for continuation of treatment

For patients who are unable to tolerate the protocol-specified dosing schedule, dose reductions are permitted at the discretion of the investigator in order to keep the patient on study drug. These changes must be recorded on the dosage administration record electronic (e)CRF.

The majority of dose reductions, modifications, interruptions are covered in [Section 6.3](#) and with further details in [Table 6-4](#). For all cases where a dose adjustment is considered necessary, but is not covered in the following sections, the investigator will send a written request to Novartis. The request must justify the dose change and provide all supportive clinical and laboratory information for complete evaluation by Novartis. Any dose adjustment for reasons not included in this section needs to be authorized by Novartis. A written reply will be promptly sent back to the investigator by Novartis.

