6.3 Dose modifications

6.3.1 Dose modification and dose delay

For patients who do not tolerate the protocol-specified dosing schedule, dose interruptions and/or reductions are either recommended or mandated in order to allow patients to continue the study treatment.

These dose modifications are summarized in [Table 6-4](#). Deviations to mandatory dose interruptions and/or reductions are not allowed. Permanent treatment discontinuation is mandatory for specific events indicated as such in [Table 6-4](#) or listed in [Section 7.1.5](#).

These dose changes must be recorded on the Dosage Administration Record CRF.

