6.3.1.7 Increased liver enzyme levels

If there is a persistent and progressive increase in serum transaminase levels (ALT/AST) that cannot be attributed to other causes, deferasirox must be interrupted. Once the cause of the liver function test abnormalities has been identified, or after a return to normal levels, cautious re-initiation of deferasirox treatment at a lower dose followed by gradual dose escalation may be considered. In cases of a second rise in serum transaminase levels, the investigator should contact Novartis. Refer to table 6.4 for further modification, interruption guidance.

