Repeat LFTs as soon as possible, preferably within 48-72 hours from awareness of the abnormal results; monitor LFTs weekly, or more frequently if clinically indicated, until resolved to baseline or stabilization. Please refer to section 6.3.3 for additional details on follow-up of toxicities.

Combined elevations of AST or ALT and total bilirubin

For patients with normal baseline ALT or AST or total bilirubin value:

AST or ALT >3.0xULN combined with total bilirubin >2.0 x ULN without evidence of cholestasis

OR

[AST or ALT>2x baseline AND > 3.0 xULN] OR [AST or ALT > 8.0 xULN], whichever is lower, combined with [total bilirubin >2x baseline AND >2.0 xULN]

Interrupt study treatment.

Permanently discontinue patient from study drug treatment if no other plausible explanation can be found for the combined increase.

Repeat as soon as possible, preferably within 48 hours from awareness of the abnormal results, then with weekly monitoring of LFTs, or more frequently if clinically indicated, until AST, ALT, or bilirubin have resolved to baseline or stabilization.

Please refer to section 6.3.3 for additional details on follow-up of toxicities.

Hepatic impairment

Moderate hepatic impairment (Child- Pugh Class B

The study medication will be interrupted and patient monitored. If liver disease prognosis improves, deferasirox can be reintroduced at 7 mg/kg/day for FCT or 50% of previous dose, whichever is less. While monitoring continues, dose may be increased by 3.5 mg/kg/day for FCT every 2 weeks, to a maximum of 50% of patient's previous dose if the investigator determines that dose increase is in the best interest of the patient. Study medication must be used with caution in such patients.

In patients who develop severe hepatic impairment (Child-Pugh Class C) during the study

Study medication must be discontinued.

Other recommended dose modifications**Changes in Serum Ferritin**

500 – 1000 ng/mL

The dose of deferasirox FCT should be adjusted as necessary every 3 months based on the trends in serum ferritin and investigator's judgement.

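### Minor: for a combined transaminase and bilirubin rise without cholestasis, Protocol Section 6.3.3.1 discontinues study drug outright, while Table 6-4 interrupts it and makes the stop permanent only if no other cause is found

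*Protocol*

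**What the plan says.** Three parts of the Protocol bear on the action.

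- **Section 6.3.3.1** (potential drug-induced liver injury). When the combined AST/ALT and bilirubin criteria are met without cholestasis, "these patients should be immediately discontinued from study drug treatment", and liver tests are repeated, preferably within 48 hours. The section does ask about an alternative cause, but only when deciding whether the case is medically significant and reported as an SAE.
- **Table 6-4**, row on combined elevations. The first action is to interrupt. The second is conditional: "Permanently discontinue patient from study drug treatment if no other plausible explanation can be found for the combined increase". The row ends: "Please refer to section 6.3.3 for additional details on follow-up of toxicities".
- **Glossary**, entry for study treatment discontinuation: "Point/time when patient permanently stops taking study treatment for any reason".

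Two further sections affect how these are read together. Section 6.3.1 says "Permanent treatment discontinuation is mandatory for specific events indicated as such in" Table 6-4 or listed in Section 7.1.5. Section 6.3.3, the parent of 6.3.3.1, keeps the two actions apart: "Patients whose treatment is interrupted or permanently discontinued due to an adverse event or abnormal laboratory value must be followed" for at least 30 days.

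**The concern.** A stopping rule for a serious liver signal in children aged 2 to 5 should have one reading. An investigator who follows Table 6-4 correctly is sent on to Section 6.3.3 for follow-up, and there meets an instruction that omits the table's condition.

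The choice has practical results. Under Section 7.1.5, discontinuation brings an end-of-treatment visit within 7 days and registration in IRT. Under Section 7.1.5.1 the child is not replaced. It also decides where the case is reported. AEs leading to discontinuation form part of a secondary safety endpoint, and SAP Section 2.11.1 tabulates them separately from AEs requiring dose adjustment or interruption.

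**Working it through.** No plan figure is involved, so the check compares the texts.

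**Step 1: the shared trigger.** For a child whose ALT, AST and bilirubin are all normal at baseline, both places use AST or ALT > 3.0 x ULN with total bilirubin > 2.0 x ULN, and both act only in the absence of cholestasis. The child therefore falls under both rules.

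**Step 2: the actions at that trigger.**

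| Result of the search for a cause | Table 6-4 | Section 6.3.3.1, with the glossary meaning |
|---|---|---|
| No other cause found | Interrupt, then stop permanently | Stop permanently |
| Another cause found | Interrupt only | Stop permanently |

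The rows agree in the first case and conflict in the second.

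**Step 3: is the permanent reading of 6.3.3.1 the better one?** The glossary says so. Elsewhere in Table 6-4, for example for AST or ALT above 20 x ULN, an unqualified instruction to discontinue appears to mean a lasting stop. The severe-rash text in Section 6.3.1.6.2 uses the same verb for a temporary stop, but it states when the stop ends and the dose for resumption. Section 6.3.3.1 gives neither.

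**Step 4: outside the shared trigger.** The printed criteria differ in three ways.

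- *Baseline condition.* For the first criterion, 6.3.3.1 requires normal ALT **and** AST **and** bilirubin; Table 6-4 says **or**. Take a child with normal transaminases and baseline bilirubin at the screening ceiling of 1.5 x ULN (exclusion criterion 8). Under 6.3.3.1 the elevated-baseline criterion applies, and bilirubin must exceed 2 x 1.5 = 3.0 x ULN. Under the table read literally, the first criterion applies and 2.0 x ULN is enough.
- *Lower-of clause.* Table 6-4 adds that the lower transaminase threshold applies; 6.3.3.1 does not. Since both already join the alternatives with OR, this is probably a difference of wording only.
- *Cholestasis.* Section 6.3.3.1 applies the exclusion to both criteria. Table 6-4 attaches it to the first only.

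**Step 5: size.** At the planned minimum of 40 children, one child moved between the discontinuation and interruption tables changes each percentage by 1/40 = 2.5 points. This is the effect per case, not a forecast of cases.

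**The case against.** The strongest reply is that 'discontinued' in Section 6.3.3.1 need not mean permanently. The glossary defines a noun phrase, the rash text uses the verb for a temporary stop, and where permanence matters the Protocol often says so. Section 6.3.3.1 omits the qualifier and moves straight to repeat tests and a search for cause. 'Stop now and investigate' is thus a tenable reading, and it fits Table 6-4. What stands is that the text is ambiguous. The permanent reading remains the better one for the reasons in Step 3, and a stopping rule open to both readings still needs correcting.

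A second reply is that Table 6-4 already governs. Section 6.3.1 supports using it as the reference for mandatory permanent stops and forbids departures from mandatory interruptions, and 6.3.3.1 says only 'should'. A reader might infer that the table overrides 6.3.3.1. The documents do not go that far: Section 6.3.1 also names Section 7.1.5, which lists general reasons for stopping, and nothing expressly sets 6.3.3.1 aside.

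A third reply is that the sponsor can settle individual cases. Section 6.1.4 says "Any dose adjustment for reasons not included in this section needs to be authorized by Novartis", but that route is for adjustments the text does not cover. This one is covered twice, differently, and Section 12 bars requests to approve deviations.

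It is fair to add that the table's cross-reference is for follow-up, not for the dosing action, and that SAP Section 2.11.5.4 calls hepatic cases rare for this compound. Both limit the weight of the point.

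**Conclusion.** The wording is wrong as it stands, and the point is minor. At the shared trigger the instructions conflict for a child in whom another cause is found. This rests on the glossary meaning of discontinuation; on the looser reading it becomes an ambiguity with the same remedy.

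Three stronger readings are not supported. A reader might infer that a child's immediate safety is at risk, but dosing stops at once and liver tests are repeated under both texts. A reader might infer that the primary result is affected, but the definition and method of the primary GI analysis do not depend on which rule is followed. And a reader might infer that the texts agree everywhere apart from this one case, but the printed triggers also differ, although the layout of the table may account for part of that.

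The remaining effect is whether such a child may resume study drug and which table counts the case. No frequency is claimed, because the documents give none.

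**What to change.** In Section 6.3.3.1, replace the unconditional instruction with: *study treatment must be interrupted immediately, and permanently discontinued if no other plausible explanation is found (see Table 6-4)*. If the sponsor intends a permanent stop in every case, amend the Table 6-4 row instead.

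In the same edit, use identical trigger wording in both places: one baseline condition ('and' or 'or'), one treatment of the lower-of clause, and the cholestasis exclusion applied to both criteria.

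No restart conditions are proposed here. In particular, the route in Section 6.3.1.7 should not be carried over by default. It concerns transaminase rises, and its alternative trigger, "or after a return to normal levels, cautious re-initiation of deferasirox treatment at a lower dose", would allow a restart with no cause identified, against Table 6-4.

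The cost is one sentence plus matching of the criteria, in a protocol amendment. No new data, visits or analyses are needed.

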6.3.4 Anticipated risks and safety concerns of the study drug

Appropriate eligibility criteria, as well as specific dose modification and stopping rules are included in this protocol. Recommended guidelines for prophylactic or supportive treatment for expected toxicities, including management of study-drug induced AEs i.e., gastrointestinal, skin toxicity and diarrhea are provided in [Table 6-4](#). Refer to preclinical toxicity and or clinical data found in the Investigator’s Brochure.

6.4 Concomitant medications

The patient must be told to notify the investigational site about any new medications he/she takes after the start of the study drug. All medications (other than study drug) and significant non-drug therapies (including physical therapy and herbal/natural medications) administered during the study must be listed on the Concomitant Medications or the Procedures and Significant Non-Drug Therapies CRF. Blood transfusions must be entered on the Blood Component Transfusion CRF

6.4.1 Blood transfusion

History of blood transfusions within the period of 3 months prior to Screening visit 1 must be recorded on Blood Component Transfusion CRF page. Additionally, record of blood transfusion during the study must be collected (see [Table 7-1](#)) and entered on the Blood Component Transfusion CRF page.

6.4.2 Permitted concomitant therapy requiring caution and/or action

The concomitant administration of deferasirox and vitamin C has not been formally studied. Doses of vitamin C up to 200 mg/day have not been associated with any adverse consequences.

Aluminum containing antacid therapies should be avoided because they may bind to deferasirox.

The concomitant use of deferasirox with potent UGT inducers (e.g. rifampicin, phenytoin, phenobarbital, ritonavir) may result in a decrease in deferasirox efficacy.

Concomitant use of any iron chelation therapy other than the study drug, investigational agents or bile acid sequestrants is not allowed.

Caution must be exercised in patients who are taking study drug in combination with the following drugs:

- Concomitant administration of deferasirox with drugs that have known ulcerogenic potential such as non-steroidal anti-inflammatory drugs, corticosteroids, or oral bisphosphonates, and use of deferasirox in patients receiving anticoagulants may increase the risk of gastrointestinal irritation

- Deferasirox, as a weak CYP3A4 inducer, may potential increase serum levels of substances metabolized through CYP3A4 (e.g. cyclosporine, simvastatin, hormonal contraceptive agents)
- Deferasirox is a moderate inhibitor of CYP2C8 and therefore, may increase serum concentrations of substances metabolized through CYP2C8 (e.g. repaglinide, pa paclitaxel)

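### The CYP3A4 caution in Protocol 6.4.2 contradicts itself: it calls deferasirox an inducer yet predicts higher substrate levels, so sites cannot tell which change in exposure to look for

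*Protocol*

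**What the plan says.** Protocol 6.4.2 covers co-medications that are allowed but need care. It makes three statements about enzyme effects:

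- On UGT: "The concomitant use of deferasirox with potent UGT inducers (e.g. rifampicin, phenytoin, phenobarbital, ritonavir) may result in a decrease in deferasirox efficacy".
- On CYP3A4: "Deferasirox, as a weak CYP3A4 inducer, may potential increase serum levels of substances metabolized through CYP3A4". The examples given are "e.g. cyclosporine, simvastatin, hormonal contraceptive agents".
- On CYP2C8, in the next bullet: "Deferasirox is a moderate inhibitor of CYP2C8 and therefore, may increase serum concentrations of substances metabolized through CYP2C8".

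The two CYP bullets come under the lead-in "Caution must be exercised in patients who are taking study drug in combination with the following drugs", so they are instructions to sites and not background text. I found no other mention of CYP3A4 in the protocol or the SAP. The list of prohibited therapies in Protocol 6.4.3 does not include CYP3A4 substrates.

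**The concern.** In a caution of this kind, the direction is the part an investigator can use. It says whether to be alert to too much or too little of the co-administered drug. Here the mechanism points one way and the stated result the other. An investigator who goes by the word inducer and one who goes by the word increase would look for opposite problems in the same child.

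The protocol gives sites nothing else with which to settle the matter. Pharmacokinetics is marked not applicable (7.2.4), and the laboratory plan in Table 7-2 includes no co-medication levels. One of the three named examples, cyclosporine, is an immunosuppressant, so for that drug the direction is not a trivial detail.

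What is at stake is the clarity of a safety instruction in a post-authorisation safety study of young children. The study's estimates are not at stake.

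**Working it through.** No arithmetic applies. The check is whether the section uses its own terms consistently.

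**Step 1. Set the three statements side by side.**

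| Enzyme | Stated mechanism | Drug affected | Stated direction |
|---|---|---|---|
| UGT | induction, by the co-medication | deferasirox | decrease: "may result in a decrease in deferasirox efficacy" |
| CYP2C8 | inhibition, by deferasirox | the co-medication | increase |
| CYP3A4 | induction, by deferasirox | the co-medication | increase |

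**Step 2. Derive the section's own rule.** The first row links induction to a smaller effect of the drug being metabolised. The second links inhibition to higher concentrations and presents this as a consequence of the mechanism. The roles differ (deferasirox is the affected drug in the first row and the acting drug in the second), and the first row speaks of efficacy where the second speaks of concentrations. Neither difference reverses the direction that each mechanism is given.

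**Step 3. Apply the rule to CYP3A4.** An inducer should give a decrease, and an increase should come from an inhibitor. The third row pairs an inducer with an increase. It is the only one of the three in which mechanism and direction do not match.

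**Step 4. Look for a correction elsewhere.** There is no second CYP3A4 statement in the protocol or SAP. Amendment 1 reports that typographical errors and inconsistencies were corrected in various sections, but the sentence remains in the current text. It is complete and legible, with no sign of redaction or of damage in reading the PDF.

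**Step 5. Ask whether the documents show which half is wrong.** They do not. Changing the mechanism would make the sentence consistent, and so would changing the direction.

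**Step 6. Trace the consequences for the analysis.** The primary endpoint is the proportion of children with selected gastrointestinal disorders (Protocol 10.4.1, SAP 2.8.1). In 6.4.2 the caution that bears on that endpoint is the separate bullet on ulcerogenic drugs and anticoagulants, which is coherent. The CYP3A4 bullet enters no eligibility criterion, study-drug dose rule, analysis set, sample-size statement or SAP output.

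**The case against.** The strongest reply is that this is a drafting slip in a bullet list that has others: the same sentence has a grammatical error, and the next bullet contains a stray fragment before a drug name. Several parts of that reply stand.

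- **The alert survives.** The named drugs are flagged for caution whichever word is wrong. Only the direction is lost.
- **No monitoring is reversed.** A reader might infer that sites would be monitoring the wrong risk. The protocol prescribes no levels, thresholds or actions for CYP3A4 substrates, so there is no prescribed monitoring to reverse.
- **The affected group may be empty.** A reader might picture a child on cyclosporine who is harmed. No passage says that any eligible child takes it, and simvastatin and hormonal contraceptives are unlikely at 2 to under 6 years. One could assume that 0 to 10% of the minimum 40 children take such a drug, which gives 0 to 0.10 × 40 = 4. Nothing in the documents supports the upper figure, and the range includes zero.
- **Sites have other references.** Protocol 8.5 points to the Investigator's Brochure for warnings. The protocol summary says that eligibility, dosing standards and safety assessments accord with the EU label.

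The last argument goes only so far. Those sources are not available here, so they cannot be credited with curing the sentence, and a correct external reference does not excuse an instruction that contradicts itself. The core of the point is unaffected: the sentence is inconsistent with the section around it, and nothing in the two documents repairs it.

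**Conclusion.** The inconsistency is established from the text of 6.4.2 alone. From the protocol, a site cannot tell whether deferasirox is expected to raise or lower exposure to the named CYP3A4 substrates. That is an internal inconsistency in safety guidance; no design decision is in question.

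Its practical reach is low. The number of children concerned is not given and may be zero, and no endpoint, sample-size statement or SAP analysis changes. That a site would be misled is an inference from where the bullet stands; the documents do not show it.

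A reader might also want to conclude that one particular word is the error, for instance that the direction was carried over from the CYP2C8 bullet. The documents do not decide this, and this review takes no position on it.

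**What to change.** Reconcile the mechanism and the direction in the CYP3A4 bullet of Protocol 6.4.2 against the Investigator's Brochure and the EU label, and correct whichever half those sources show to be wrong. Send sites the corrected sentence as a clarification, so that the expected direction is clear for each named example.

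The cost is one sentence in the protocol and a short letter to sites. No data collection, analysis or SAP text needs to change. If the sponsor wants to know whether any child was concerned, concomitant medications are already recorded on the CRF (Protocol 6.4) and listed by ATC class (SAP 2.7), so a review of that listing would answer the question without new data.
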